**Plan for statistical analysis of efficacy and safety parameters**

*Table 8. Urinalysis values during the trial (template)*

Indicator	Visit		
	Mexitol®	Placebo	Mexitol®+ Placebo
Normal	Abs.		
	%		
Deviations from normal (clinically insignificant)	Abs.		
	%		
Deviations from normal (clinically significant)	Abs.		
	%		
Inter-group differences	Statistical criterion	p-level	

*Table 9. Results of the medical examination during the trial (template)*

Indicator	Investigational product		
	Visit 1 (Day -14 -1)	Visit 5 (Day 43+1)	Visit 6 (Day 50+3)
Normal	Abs.		
	%		
Deviations from normal (clinically insignificant)	Abs.		
	%		
Deviations from normal (clinically significant)	Abs.		
	%		
Comparison of drugs (statistical test  ) (p-value)			

*Table 10. Comparison of vital signs when taking the investigational product and the comparator product (template)*

Indicator	Investigational product		
	Visit 1 (Day -14 -1)	Visit 5 (Day 43+1)	Visit 6 (Day 50+3)
N			

 Applicable for categorical indicators

 General condition

- Skin condition

- Musculoskeletal system

- Lymph nodes

- Thyroid gland

- Upper respiratory tract and lungs

- Heart, blood vessels

- Abdominal organs, kidneys

- Neuropsychiatric status

 Pearson's  $\chi^2$  test/Fisher's exact test

 BP, HR, RR.

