## Plan for statistical analysis of efficacy and safety parameters

classification objectives). The protocol provides for the recording of all AEs that occur to the patient after the first administration of the trial therapy and until the end of the patient's participation in the trial. Frequency tables with data on discontinuation of therapy or changes in therapy parameters due to AEs will be presented. The choice of statistical criterion will be determined by the conformity/nonconformity to the normal distribution law and the dependence/independence of the samples being compared. Comparisons of safety performance between trial groups will be made using the  $\chi^2$ -square test (for qualitative data) and the t-test for data whose distribution follows the law of normal distribution, or its non-parametric analogue (for data whose distribution does not follow the law of normal distribution). The Mann-Whitney U-test will be used as the non-parametric analogue of the t-criterion.

Data obtained before the start and at the end of the trial will be compared to assess safety parameters.

To assess the robustness of the trial results, a sensitivity analysis will be performed on the main efficacy parameter: "Mean change in the total score on the inattention, hyperactivity/impulsivity subscale of the SNAP-IV scale after 6 weeks of therapy vs. baseline".

Since sensitivity analysis aims to assess the impact on the trial results of deviations from the methods of analysis used, as well as the impact of missing data values and a priori assumptions in order to identify the results that are most dependent on questionable or untenable assumptions, this trial includes an assessment of the impact of the following factors on the main conclusion of the trial:

- **Investigational site:** planned analysis adjusted for the covariate "Site" using a generalized linear model (GLM) to assess the consistency of the results with the analysis without introducing one;
- **Analysed populations:** in addition to the main analysis in the FAS population, a secondary analysis in the PP population is planned to assess the consistency of the results with the main analysis;

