## **10. Safety analysis**

The protocol provides for the recording of all AEs that occur to the patient after the first administration of the trial therapy and until the end of the patient's participation in the trial. AEs will be coded according to the Medical Dictionary for Regulatory Activities (MedDRA). Further analysis of AEs, including SAEs, will consist of determining the total number of AEs, total number of patients with AEs, number of AEs associated with the trial therapy, number of AEs that required cancellation of therapy or changes in therapy parameters, and number of patient-initiated dropouts.

The frequency and severity of both all AEs and drug-related AEs (i.e., with an estimated association of at least "possible") will be presented for system organ classes (SOC - System Organ Class MedDRA - the highest level of classification of AEs, taking into account etiology, localization of manifestations and classification objectives).

Frequency tables with data on discontinuation of therapy or changes in therapy parameters due to AEs will be presented.

Data obtained before the start and at the end of the trial will be compared to assess safety parameters.

The statistical report on the results of this trial will include tables showing the dynamics of clinical manifestations and instrumental examination data, the dynamics of vital functional parameters and comparison of the results of clinical and biochemical blood analysis and general urine analysis. The results of the evaluation of the incidence of adverse events will be given.

The following safety assessment parameters will be analysed: the number of adverse events (AEs) and serious AEs (SAEs) and the incidence of AEs/SAEs associated with the investigational product/placebo.

All data will be analyzed on the safety population.

The identification of AEs, including serious AEs, will consist of determining the total number of AEs;

- total number of patients with AEs;
- number of AEs with a possible and higher degree of association with the investigational product/procedure;
- number of AEs that required discontinuation of therapy;

The frequency and severity of all AEs and drug-related AEs (i.e., with an estimated association of at least "possible"), will be summarized for body systems. Data on patient dropouts from the trial due to the development of AEs (if any) will be tabulated.

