### **Plan for statistical analysis of efficacy and safety parameters**

homogeneity, etc. is not known in advance. During the course of the analysis, the list of methods to be used may be modified and supplemented if necessary for the qualitative processing of the data. All deviations from the statistical plan of the survey as well as their causes will be detailed in the statistical report.

Vital signs will also be presented with descriptive statistics showing changes from baseline.

Data harmonisation, if possible, will be done by converting values to commonly used or most common units of measurement in the dataset. In case the units of measurement cannot be harmonised, the data will be presented as tables without further statistical treatment.

Based on the results of the trial, after the final statistical analysis, a conclusion will be made about the efficacy and safety of Mexidol® vs. placebo.

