**Plan for statistical analysis of efficacy and safety parameters**

Indicator 	Investigational product		
	Visit 1 (Day -14 -1)	Visit 5 (Day 43+1)	Visit 6 (Day 50+3)
Mean			
95% CI, L			
95% CI, U			
Median			
Min			
Max			
Q 1			
Q 3			
Range			
QRange			
SD			
CV			
Intragroup comparison: comparison of data at the end of therapy with data at the start of therapy (statistical criterion  ) (p-level value)			
Comparison of drugs (statistical test  ) (p-value)			
Indicator span diagram/ indicator scatter diagram			

*Table 11. Results of statistical analysis of blood and urine test results (template)*

Indicator 	Investigational product	
	Visit 1 (Day -14 -1)	Visit 5 (Day 43+1)
N		
Mean		
95% CI, L		
95% CI, U		
Median		
Min		
Max		
Q 1		
Q 3		
Range		
QRange		
SD		
CV		
Intragroup comparison: comparison of data at the end of therapy with data at the start of therapy (statistical criterion  ) (p-level value)		
Comparison of drugs (statistical test  ) (p-value)		
Indicator span diagram/ indicator scatter diagram		

 T-test for related samples or Wilcoxon test depending on the type of distribution of the indicator

 T-test for independent samples or Mann-Whitney test depending on the type of distribution of the indicator

 Interval indicators measured according to the clinical trial protocol

 T-test for related samples or Wilcoxon test depending on the type of distribution of the indicator

 T-test for independent samples or Mann-Whitney test depending on the type of distribution of the indicator

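### SAP Table 10 has no place for the vital-sign changes that SAP section 10 says will be described, and its between-arm test, as laid out, makes no use of each child's Visit 1 value

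*SAP*

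**What the plan says.** SAP section 10 commits to a description of change: "Vital signs will also be presented with descriptive statistics showing changes from baseline". The template for these data is Table 10 in SAP section 12, "Comparison of vital signs when taking the investigational product and the comparator product (template", which covers blood pressure, heart rate and respiratory rate. Its columns are Visit 1 ("Visit 1 (Day -14 -1"), Visit 5 and Visit 6. There is no change column. Tables 3 and 4, for efficacy, do have one for each arm, in absolute and percentage terms.

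Table 10 has two test rows:

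- Within an arm: "Intragroup comparison: comparison of data at the end of therapy with data at the start of therapy", by a paired t-test or Wilcoxon test.
- Between arms: "Comparison of drugs (statistical test", which its footnote defines as "T-test for independent samples or Mann-Whitney test depending on the type of distribution of the indicator". No covariate is named.

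The running text does not settle which variable is compared. SAP section 6 begins "Comparisons of safety performance between trial groups will be made using the" and then lists the chi-square test and the t-test or its non-parametric analogue, without naming visit values or changes. SAP section 10 adds: "Data obtained before the start and at the end of the trial will be compared to assess safety parameters". That describes a before-and-after comparison and does not say that the change is compared between arms. Protocol 4.5.2 and the visit schedule show that blood pressure, heart rate and respiratory rate are recorded at screening.

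**The concern.** Two things do not line up. First, the change statistics announced in section 10 have no cell in the template meant to carry them. Second, the natural safety question is whether vital signs moved more on either dose than on placebo. The row that uses the child's own starting value has no placebo control, and the row that has a placebo control does not, as laid out, use the starting value.

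The stake is precision. Stable differences between children enter the two-sample test as noise, and any chance difference between arms at Visit 1 is partly carried into the Visit 5 and Visit 6 results. Table 10 also gives confidence limits for each column's mean but none for the difference between arms. A non-significant p-value from an imprecise test could then be read as reassurance.

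**Working it through.** **Which variable is tested.** No sentence says. The columns are visit values, and the footnote chooses the test by the distribution of the indicator. Table 2, which lists the distributions to be checked, has heart rate and systolic and diastolic blood pressure at each visit, with no row for a change. The natural reading is therefore a test on visit values, and nothing in the SAP says otherwise.

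**Number per arm.** The documents give no figure for vital signs, so the primary-endpoint sample size sets the scale. With a difference of 2.5, pooled SD 6.27, two-sided 0.05 and 80% power, n = 2 × 6.27² × (1.96 + 0.842)² / 2.5² = 98.7, so 99. The t-distribution gives 100 (power 80.1%), which matches the stated 100 completers. 100 / 0.9 = 111.1, stated as 111 randomised per arm.

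**Assumptions not in the documents.** Systolic SD 10 mmHg at each visit, a true shift of 3 mmHg for the power figures, and a Visit 1 to Visit 5 correlation r of 0.3 to 0.7. The formulas use a normal approximation.

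**Formulas.** SE = 10 × √(v × 2/100), half-width = 1.96 × SE, and power = Φ(3/SE − 1.96). The variance factor v is 1 for visit values, 2(1 − r) for a change score and 1 − r² for adjustment for Visit 1.

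| r | Visit value: half-width, power | Change score: half-width, power | Adjusted for Visit 1: half-width, power |
|---|---|---|---|
| 0.3 | 2.77, 56% | 3.28, 43% | 2.64, 60% |
| 0.5 | 2.77, 56% | 2.77, 56% | 2.40, 69% |
| 0.6 | 2.77, 56% | 2.48, 66% | 2.22, 76% |
| 0.7 | 2.77, 56% | 2.15, 78% | 1.98, 84% |

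Half-widths are in mmHg and scale with the SD. At SD 8 the visit-value figure is 2.77 × 0.8 = 2.22, and at SD 12 it is 2.77 × 1.2 = 3.33. The relative gain from adjustment, 1 − √(1 − r²), does not depend on the SD: 5%, 13%, 20% and 29% at r = 0.3, 0.5, 0.6 and 0.7.

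**Chance imbalance.** With 111 per arm, the SE of the Visit 1 difference between two given arms is 10 × √(2/111) = 1.34 mmHg. The probability of a difference of at least 2 mmHg in either direction is 0.136, since 2/1.34 = 1.49. The visit-value comparison at Visit 5 keeps on average r times that difference: 1.0, 1.2 or 1.4 mmHg at r = 0.5, 0.6 or 0.7.

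**The case against.** The strongest reply is that this is a gap in a table shell. Section 10 promises descriptive change statistics and no between-arm test of change, and a template without a change column does not cancel the text. A reader might infer that the SAP contradicts itself on the test. It does not; the mismatch is confined to the missing display. The visit-value reading also rests on layout. The template shows one product heading over the visit columns, and the test cells are empty.

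A reader might also infer that Table 10 is the only comparison with placebo that takes the starting state into account. The documents do not support that. Protocol 8.2.2 has new abnormalities, or worsening relative to screening, classified as adverse events, and SAP Table 15 compares adverse-event incidence across the three arms with a p-value. That route does not estimate a mean shift, but clinically noticed worsening does reach a placebo comparison. Nor is Visit 1 discarded: it is a column of Table 10 and feeds the paired row.

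Finally, the precision gain belongs to baseline adjustment, which the SAP does not promise for vital signs. The change score that section 10 describes would, if tested, gain nothing at r = 0.5 and lose below it.

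All of this stands and limits the point. It does not supply the missing change columns, and it does not make an unadjusted test the better use of values already collected.

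**Conclusion.** The point holds as a limited one. Table 10 lacks the change description announced in SAP section 10. Its between-arm row, on the natural reading, is an unadjusted two-sample test on visit values. It would be wrong to conclude that this comparison is biased: randomisation keeps it unbiased on average. The cost is precision and exposure to chance imbalance.

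Under the assumed SD of 10 mmHg and 100 per arm, adjustment narrows the half-width from 2.77 mmHg to between 2.40 and 1.98 for r of 0.5 to 0.7; at r = 0.3 the gain is small (2.64). The SD, the correlation and the 3 mmHg shift are assumptions, so the direction is firmer than the size. The listed safety endpoints are counts, frequency and severity of adverse events, so neither they nor the primary endpoint are affected. The change is worth making because it costs almost nothing, and the trial's main conclusion does not depend on it.

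**What to change.** In Table 10, add change from Visit 1 at Visit 5 and at Visit 6 for each arm, as description. State in the SAP which variable the between-arm row compares. Base that row on each dose minus placebo, with a 95% CI, from a linear model for the Visit 5 or Visit 6 value adjusted for the Visit 1 value. Do not use a bare change-score test, which loses precision when the correlation is below 0.5. Keep the visit values as description. Table 11 (laboratory values) has the same layout, although section 10 also announces changes from baseline there, so the same edit can be made at the same time.

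The cost is some SAP wording and two columns per arm, with no new data, visits or patients.

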**Version 1.0 of 27.9.2019**

Protocol-specific version for protocol #PHS-ADHD-002-MEX- TAB, version 3.0 dated 19.07.2019.

**CONFIDENTIAL**

page 36 of 42

**Plan for statistical analysis of efficacy and safety parameters**

Indicator 	Investigational product		
	Visit 1 (Day -14 -1)	Visit 5 (Day 43+1)	Visit 6 (Day 50+3)
Mean			
95% CI, L			
95% CI, U			
Median			
Min			
Max			
Q 1			
Q 3			
Range			
QRange			
SD			
CV			
Intragroup comparison: comparison of data at the end of therapy with data at the start of therapy (statistical criterion  ) (p-level value)			
Comparison of drugs (statistical test  ) (p-value)			
Indicator span diagram/ indicator scatter diagram			

*Table 11. Results of statistical analysis of blood and urine test results (template)*

Indicator 	Investigational product	
	Visit 1 (Day -14 -1)	Visit 5 (Day 43+1)
N		
Mean		
95% CI, L		
95% CI, U		
Median		
Min		
Max		
Q 1		
Q 3		
Range		
QRange		
SD		
CV		
Intragroup comparison: comparison of data at the end of therapy with data at the start of therapy (statistical criterion  ) (p-level value)		
Comparison of drugs (statistical test  ) (p-value)		
Indicator span diagram/ indicator scatter diagram		

 T-test for related samples or Wilcoxon test depending on the type of distribution of the indicator

 T-test for independent samples or Mann-Whitney test depending on the type of distribution of the indicator

 Interval indicators measured according to the clinical trial protocol

 T-test for related samples or Wilcoxon test depending on the type of distribution of the indicator

 T-test for independent samples or Mann-Whitney test depending on the type of distribution of the indicator

**Version 1.0 of 27.9.2019**

*Protocol-specific version for protocol #PHS-  
ADHD-002-MEX- TAB, version 3.0 dated  
19.07.2019.*

**CONFIDENTIAL**

page 37 of 42

## Plan for statistical analysis of efficacy and safety parameters

Table 12. Summary table of the incidence of reported AEs in the group taking Mexidol by severity with randomization numbers of patients (N=)

AE/code, PT according to MedDRA version	Mild AE		Medium AE		Moderate AE		Life-threatening AE		Fatal AE		Total		Total R+UR
	R	UR	R	UR	R	UR	R	UR	R	UR	R	UR	
Eyes													
Cataract/10007739 Cataracta			1  /6116 								1		1
Vascular system													
Hypertensive crisis/10020802						1/7938 					1		1
...													

Table 13. Summary table of the incidence of reported AEs in the group taking placebo by severity with randomization numbers of patients (N=)

Adverse eventcode PT level according to MedDRA version	Mild AE		Medium AE		Moderate AE		Life-threatening AE		Fatal AE		Total		Total R+UR
	R	UR	R	UR	R	UR	R	UR	R	UR	R	UR	
Eyes													
...													
Vascular system													
...													

 R - AE related to the investigational product; UR - AE unrelated to the investigational product; R+UR - sum of related and unrelated AEs; nm - degree of relationship, where n is the number of AEs; m 1 - definite relationship; m 2 - probable relationship; m 3 - possible relationship

 13/6116 means - one AE with a degree of possible relationship; 6116 - the patient's randomisation number

 1/7938 means - one unrelated AE, 7938 - randomization number of the patient

 R - AE related to the investigational product; UR - AE unrelated to the investigational product; R+UR - sum of related and unrelated AEs; nm - degree of relationship, where n is the number of AEs; m 1 - definite relationship; m 2 - probable relationship; m 3 - possible relationship; for an example of filling in, see Table 12

**Version 1.0 of 27.9.2019**

Protocol-specific version for protocol #PHS-ADHD-002-MEX- TAB,  
version 3.0 dated 19.07.2019.

**CONFIDENTIAL**

page 38 of 42

## Plan for statistical analysis of efficacy and safety parameters

Table 14. Summary table of the incidence of reported AEs in the group taking Mexidol = placebo by severity with randomization numbers of patients (N=)

Adverse eventcode PT level according to MedDRA version	Mild AE		Medium AE		Moderate AE		Life-threatening AE		Fatal AE		Total		Total R+UR
	R	UR	R	UR	R	UR	R	UR	R	UR	R	UR	
Eyes													
Vascular system													
...													

Table 15. Summary table of the incidence of AEs after taking each investigational product

Adverse eventcode PT level according to MedDRA version	Mexidol N=		Mexidol+placebo N=		Placebo N=		P-value (Statistical criterion)
	n	%	n	%	n	%	
Eyes							
Vascular system							

Table 16. List of all adverse events for each patient

Site number	Randomization number, full name	Demographic data	AE/code, PT according to MedDRA version	AE onset	Severity	Seriousness	Relationship	Actions taken in relation to the patient	Actions taken in relation to the investigational product	Concomitant therapy	Date the AE resolved	Outcome
		Age, y										
		gender										

 A - AE associated with the investigational product; UR - AE unrelated to the investigational product; R+UR - sum of related and unrelated AEs; nm - degree of relationship, where n is the number of AEs; m 1 - definite relationship; m 2 - probable relationship; m 3 - possible relationship; for an example of filling in, see Table 12

Version 1.0 of 27.9.2019

Protocol-specific version for protocol #PHS-ADHD-002-MEX- TAB,  
version 3.0 dated 19.07.2019.

CONFIDENTIAL

page 39 of 42

## Plan for statistical analysis of efficacy and safety parameters

		Weight, kg											
		Height, cm											
		race											

Table 17. Classification of AEs according to MedDRA v. 22.0 RU

Randomization number, initials	AE		MedDRA AE code, SOC level		MedDRA AE term, SOC level		MedDRA AE code, PT level		MedDRA AE term, PT level	

Table 18. Summary table of the incidence of reported SAEs in the group taking Mexidol by severity with randomization numbers of patients (N= )

Adverse event/code, PT level according to MedDRA version	Mild AE		Medium AE		Moderate AE		Life-threatening AE		Fatal AE		Total		Total
	R	UR	R	UR	R	UR	R	UR	R	UR	R	UR	
Eyes													
Vascular system													
---													

Table 19. Summary table of the incidence of reported SAEs in the group taking placebo by severity with randomization numbers of patients (N= )

Adverse event/code PT level according to MedDRA version	Mexidol N=		Mexidol+placebo N=		Placebo N=		P-value (Statistical criterion)
	n	%	n	%	n	%	

 A - SAE associated with the investigational product; UR - SAE unrelated to the investigational product; R+UR - sum of related and unrelated SAEs; nm - degree of relationship, where n is the number of AEs; m 1 - definite relationship; m 2 - probable relationship; m 3 - possible relationship; for an example of filling in, see Table 12

## Plan for statistical analysis of efficacy and safety parameters

Eyes								
Vascular system								
...								

Table 20. Summary table of the incidence of reported SAEs in the group taking Mexidol+placebo by severity with randomization numbers of patients (N=)

Adverse event/code, PT level according to MedDRA version	Mild AE		Medium AE		Moderate AE		Life-threatening AE		Fatal AE		Total		Total
	R	UR	R	UR	R	UR	R	UR	R	UR	R	UR	R+UR
Eyes													
Vascular system													
...													

Table 21. Summary table of the incidence of SAEs after taking each investigational product

Adverse event/code PT level according to MedDRA version	Mexidol N=		Placebo N=		P-value (Statistical criterion)
	n	%	η	%	
Eyes					
Vascular system					
...					

Table 22. A list of all serious adverse events for each patient

Site number	Randomization number, full name	Demographic data	SAE/code, PT according	AE onset	Severity	Seriousness	Relationship	Actions taken in relation	Actions taken in relation to	Concomitant therapy	Date the AE resolved	Outcome

 A - SAE associated with the investigational product; UR - SAE unrelated to the investigational product; R+UR - sum of related and unrelated SAEs; nm - degree of relationship, where n is the number of AEs; m 1 - definite relationship; m 2 - probable relationship; m 3 - possible relationship; for an example of filling in, see Table 12

Version 1.0 of 27.9.2019

Protocol-specific version for protocol #PHS-ADHD-002-MEX- TAB,  
version 3.0 dated 19.07.2019.

CONFIDENTIAL

page 41 of 42

